### **Induration**

The clinician examines the patient's leg and chooses the category that best describes the patient's skin induration. Induration refers to skin and subcutaneous changes such as chronic edema with fibrosis, hypodermatitis, white atrophy, and lipodermatosclerosis.

**None**= 0:None

**Mild**= 1:Induration that is limited to the perimalleolar area

**Moderate**= 2: Induration that involves the lower third of the calf

**Severe**= 3:Induration that involves more than the lower third of the calf

### **Active Ulcer Number**

The clinician examines the patient's leg and chooses the category that best describes the number of active ulcers.

**None**= 0:None

**Mild**= 1:1 Ulcer

**Moderate**= 2:2 Ulcers

**Severe**= 3: $\geq$ 3 Ulcers

### **Active Ulcer Duration**

If there is at least 1 active ulcer, the clinician describes the 4 categories of ulcer duration that are outlined below to the patient and asks the patient to choose, for the leg that was treated, the category that best describes the duration of the longest unhealed ulcer.

**None**= 0:No active ulcers

**Mild**= 1:Ulceration present for <3 mo

**Moderate**= 2:Ulceration present for 3-12 mo

**Severe**= 3:Ulceration present for >12 mo

### **Active Ulcer Size**

If there is at least 1 active ulcer, the clinician examines the patient's leg and chooses the category that best describes the size of the largest active ulcer.

**None**= 0:No active ulcer

**Mild**= 1:Ulcer <2 cm in diameter

**Moderate**= 2:Ulcer 2-6 cm in diameter

**Severe**= 3:Ulcer >6 cm in diameter

### **Use of Compression Therapy**

Choose the level of compliance with medical compression therapy on the leg to be treated / treated leg.

**None**= 0:Not used

**Mild**= 1:Intermittent use

**Moderate**= 2:Wears stockings most days

**Severe**= 3:Full compliance: stocking

**Revised Venous Clinical Severity Score (VCSS)**

Pain or other discomfort (i.e., aching, heaviness, fatigue, soreness, burning) Presumes venous origin	None: 0	Mild: 1 Occasional pain or other discomfort (i.e., not restricting regular daily activity)	Moderate: 2 Daily pain or other discomfort (i.e., interfering with but not preventing regular daily activities)	Severe: 3 Daily pain or discomfort (i.e., limits most regular daily activities)
Varicose Veins "Varicose" veins must be ≥3 mm in diameter to qualify in the standing position	None: 0	Mild: 1 Few: scattered (i.e., isolated branch varicosities or clusters) Also includes corona phlebectatica (ankle flare)	Moderate: 2 Confined to calf or thigh	Severe: 3 Involves calf and thigh
Venous Edema Presumes venous origin	None: 0	Mild: 1 Limited to foot and ankle area	Moderate: 2 Extends above ankle but below knee	Severe: 3 Extends to knee and above
Skin Pigmentation Presumes venous origin Does not include focal pigmentation over varicose veins or pigmentation due to other chronic diseases (i.e., vasculitis purpura)	None: 0 None or focal	Mild: 1 Limited to perimalleolar area	Moderate: 2 Diffuse over lower third of calf	Severe: 3 Wider distribution above lower third of calf
Inflammation More than just recent pigmentation (i.e., erythema, cellulitis, venous eczema, dermatitis)	None: 0	Mild: 1 Limited to perimalleolar area	Moderate: 2 Diffuse over lower third of calf	Severe: 3 Wider distribution above lower third of calf
Induration Presumes venous origin of secondary skin and subcutaneous changes (i.e., chronic edema with fibrosis, hypodermatitis) Includes white atrophy and lipodermatosclerosis	None: 0	Mild: 1 Limited to perimalleolar area	Moderate: 2 Diffuse over lower third of calf	Severe: 3 Wider distribution above lower third of calf
Active Ulcer Number	0	1	2	≥3
Active Ulcer Duration (longest active)	N/A	<3 mo	>3 mo but <1 y	Not healed for >1 y
Active Ulcer Size (largest active)	N/A	Diameter <2 cm	Diameter 2-6 cm	Diameter >6 cm
Use of Compression Therapy	0 Not used	1 Intermittent use of stockings	2 Wears stockings most days	3 Full compliance: stockings

## 13.7 Appendix G: EQ-5D-5L

## Health Questionnaire

***English version for the UK  
(validated for Ireland)***

**SAMPLE**

By placing a tick in one box in each group below, please indicate which statements best describe your own health state today.

### **Mobility**

I have no problems in walking about

I have some problems in walking about

I am confined to bed

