## 1. TERMS, ACRONYMS, ABREVIATIONS

---

The following abbreviations and specialist terms are used in this protocol.

AASV	Anterior Accessory Saphenous Vein
ABPI	Ankle-Brachial Pressure Index
ADR	Adverse Drug Reaction
AE	Adverse Event
CEAP	Clinical Etiologic Anatomic Pathophysiologic
CFR	Code of Federal Regulation
CI	Confidence Interval
CRA	Clinical Research Associate
CTA	Clinical Trial Agreement
CV	Curriculum Vitae
CVD	Chronic Venous Disorders
DCF	Data Clarification Form
DCT	Data Capture Tool
DMP	Data Management Plan
DM	Data Management
DVT	Deep Vein Thrombosis
EQ-5D-5L	EuroQol five dimension five level questionnaire
FDA	Food and Drug Administration
FPI	Full Prescribing Information
GCP	Good Clinical Practice
GSV	Great Saphenous Vein
HIPAA	Health Insurance Portability and Accountability Act
ICF	Informed Consent Form
ICH	International Conference on Harmonization
iDCT	Investigator Data Capture Tool
IFU	Instructions for Use
IRB	Institutional Review Board
IP	Investigational Product
NPRS	Numeric Pain Rating Scale
PE	Pulmonary Embolism
RCT	Randomized-Controlled Trial
QOL	Quality of Life
REB	Research Ethics Board
SAE	Serious Adverse Event
SAP	Statistical Analysis Plan
sDCT	Subject Data Capture Tool
SEPS	Sub-fascial Endoscopic Perforator Vein Surgery
SIC	Subject Identification Code
SFJ	Saphenofemoral Junction
SoC	Standard of Care
SPJ	Saphenopopliteal Junction
SSV	Small Saphenous Vein
SW	Source Worksheet
USWR	United States Wound Registry

VAS	Visual Analogue Scale
VCSS	Venous Clinical Severity Score
VLU	Venous Leg Ulcer
WCC	Wound Care Center
WHI	Wound Healing Index

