## 5.4 Secondary Endpoint(s)

---

- Percent of wounds remaining closed at 3 months ( $\pm 1\text{wk}$ ) post-wound closure date, determined via photograph assessed by Tissue Analytics®; non-healed wounds are not included in percent calculation
- For healed wounds, rate of VLU recurrence collected via phone calls and subject-collected photographs at 6 months ( $\pm 1\text{wk}$ ) and 12 months ( $\pm 1\text{wk}$ ) post-treatment
- Change in pain on NPRS compared to baseline at 12 weeks ( $\pm 1\text{wk}$ ), 6 months ( $\pm 1\text{wk}$ ), 12 months ( $\pm 1\text{wk}$ ) post-treatment
- Change on EQ-5D-5L quality of life assessment compared to baseline at 12 weeks ( $\pm 1\text{wk}$ ) and 12 months ( $\pm 1\text{wk}$ ) post-treatment
- Change in VCSS from Baseline to 12 week ( $\pm 1\text{wk}$ ) and 12 month ( $\pm 1\text{wk}$ ) follow-up
- Number of ulcer free weeks defined as weeks from time of closure (complete epithelialization is recorded) to date of recurrence or last contact if no recurrence (at study completion or withdrawal)

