### 8.2.11 EQ-5D-5L Quality of Life Assessment

---

The EQ-5D-5L is a validated, widely used quality of life assessment. It is a patient reported outcome that provides a simple descriptive profile and single index value for health status. The questionnaire consists of 5 questions pertaining to specific health dimensions, including mobility, self-care, usual activities, pain/discomfort, anxiety/depression, and overall health status rating scale. Subjects should complete questionnaire on SW and data is entered into iDCT.

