### **Anxiety/Depression**

[figure not shown]
I am not anxious or depressed

I am moderately anxious or depressed

I am extremely anxious or depressed

Best  
imaginable  
health state

100

To help people say how good or bad a health state is, we have drawn a scale (rather like a thermometer) on which the best state you can imagine is marked 100 and the worst state you can imagine is marked 0.

We would like you to indicate on this scale how good or bad your own health is today, in your opinion. Please do this by drawing a line from the box below to whichever point on the scale indicates how good or bad your health state is today.

Your own  
health state  
today

Worst  
imaginable  
health state

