3.5.2.3 Change in pain on NPRS compared to baseline

An 11-point NPRS is used to assess patient's level of pain. A patient is asked "What was your pain level at the ulcer location over the last 24 hours?" and selects a score between 0 and 10, with 0 meaning no pain and 10 meaning the worst pain.

Summary statistics for each visit time point and change from baseline for NPRS through 12 weeks, 6 months and 12 months post-treatment will be presented with 95% CI. NPRS

assessments from both the EDC and sDCT will be combined and slotted into windows found in section 3.1. If a patient has more than one assessment during a timepoint, the worst (highest) NPRS score will be used.

Additionally, NPRS assessments will be summarized using shift tables by each visit and worst value post baseline.

3.5.2.4 Change on EQ-5D-5L quality of life assessment compared to baseline at 12 weeks and 12 months post-treatment

The EQ-5D-5L is a self-administered questionnaire consisting of 5 questions pertaining to specific health dimensions (mobility, self-care, pain, usually activities and anxiety and depression), and health status rating scale (visual analogue scale [VAS]). Each dimension has 5 levels: no problems, slight problems, moderate problems, severe problems, and extreme problems. If a patient has died, the last EQ-5D-5L dimension assessment prior to death will be imputed as extreme problems (coded as 5).

The VAS records the respondent's self-rated health on a 20 cm vertical, visual analogue scale with endpoints labeled 'the best health you can imagine' (Score=100) and 'the worst health you can imagine' (Score = 0). This information can be used as a quantitative measure of health as judged by the individual respondents. If a patient has died, the last EQ-5D-5L VAS assessment prior to death will be imputed as 0.

Each one digit number expressing the level selected for each dimension can be combined into a 5-digit number describing the respondent's health state. For example, the number 11111 represents the respondent not having any problems in all five dimensions. These 5-digit numbers are health states which can be converted to an index value, where 1 represents full health and 0 is equivalent to death. A health state could be considered worse than death and the index values for those states will be less than 0. The index value will be calculated as:

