4.1 EQ-5D-5L Derivations⁴

Question	Text	Coded Value
Mobility	No problems/No pain/Not anxious	1
Self-Care	Slight problems/Slight pain/Slightly anxious	2
Usual Activities	Moderate problems/Moderate pain/Moderately anxious	3
Pain/Discomfort	Severe problems/Severe pain/Severely anxious	4
Anxiety/Depression	Unable/Extreme Pain/Extremely anxious	5

The following table will be used in calculating the index value from the 5-digit health state.

Index value = $1 - (Dimension\ 1\ Estimate + Dimension\ 2\ Estimate + Dimension\ 3\ Estimate + Dimension\ 4\ Estimate + Dimension\ 5\ Estimate)$

The dimension estimates will be taken from the table below. Each estimate corresponds to the level each respondent checked for each dimension. For example, if a patient has a health state of 23245, the following calculation will be used:

$$1 - (0.096 + 0.107 + 0.068 + 0.318 + 0.321) = 0.270$$

Constant		1.000
Mobility	None	0
	Slight	0.096
	Moderate	0.122
	Severe	0.237
	Unable	0.322
Self-care	None	0
	Slight	0.089
	Moderate	0.107
	Severe	0.220
	Unable	0.261
Usual Activities	None	0
	Slight	0.068
	Moderate	0.101
	Severe	0.255
	Unable	0.255
Pain/discomfort	None	0
	Slight	0.060
	Moderate	0.098

	Severe	0.318
	Unable	0.414
Anxiety/depression	None	0
	Slight	0.057
	Moderate	0.123
	Severe	0.299
	Unable	0.321

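### Appendix G, titled EQ-5D-5L, prints a three-level UK form, while the SAP codes and values five levels with no conversion rule; the form actually used must be confirmed before the index is scored

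*Protocol*

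**What the plan says.** The protocol's abbreviation list defines the instrument as the "EuroQol five dimension five level questionnaire". Protocol 5.4 makes it a secondary endpoint: "Change on EQ-5D-5L quality of life assessment compared to baseline at 12 weeks", and again at 12 months. On collection, Protocol 8.2.11 says: "Subjects should complete questionnaire on SW and data is entered into iDCT".

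The only questionnaire reproduced in the documents is under "Appendix G: EQ-5D-5L". It is a UK-English version marked as a sample. Each of the five dimensions has three statements. Mobility runs from no problems, through "I have some problems in walking about", to being confined to bed. Anxiety/depression ends at "I am extremely anxious or depressed", with one moderate statement between that and none. A 0-100 health scale follows.

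SAP 3.5.2.4 describes a different answer structure: "Each dimension has 5 levels: no problems, slight problems, moderate problems, severe problems, and extreme problems". SAP 4.1 codes these 1 to 5 and gives a value for each level of each dimension: "The following table will be used in calculating the index value from the 5-digit health state". The cited source of the table is a US five-level valuation. SAP 3.6 adds a misery score, the sum of the five codes. SAP section 2, which lists changes to the protocol analysis, mentions no change of instrument.

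**The concern.** The printed form cannot supply the codes that the SAP needs. It has no slight and no severe answer. Two of its phrases, *some problems* (in three dimensions) and *confined to bed*, match no SAP label. Nothing in either document says how to turn such answers into five-level codes.

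If the form was fielded, whoever entered or programmed the data had to choose a mapping, and the index would depend on that choice. The index, the dimension shift tables of Protocol 10.5 and the misery score would all be affected, as would the EQ-5D-5L summary at the interim (SAP 3.8). If different versions were used at different visits, change from baseline would mix two scales. Baseline is taken before treatment and cannot be collected again.

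**Working it through.** **Inputs.** Answer options come from Protocol Appendix G. Values come from the SAP 4.1 table, in the order mobility, self-care, usual activities, pain, anxiety:

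| Level | MO | SC | UA | PD | AD |
|---|---|---|---|---|---|
| 2 slight | 0.096 | 0.089 | 0.068 | 0.060 | 0.057 |
| 3 moderate | 0.122 | 0.107 | 0.101 | 0.098 | 0.123 |
| 4 severe | 0.237 | 0.220 | 0.255 | 0.318 | 0.299 |
| 5 unable/extreme | 0.322 | 0.261 | 0.255 | 0.414 | 0.321 |

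Formula (SAP 3.5.2.4): index = 1 - sum of the five values.

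**The SAP's own example.** For state 23245 the values sum to 0.096 + 0.107 + 0.068 + 0.318 + 0.321 = 0.910, so the index is 0.090. The SAP prints 0.270. The five terms agree with the table, so this is a slip in the arithmetic. It is a separate matter and does not affect what follows.

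**Answer structure.** The form allows 3^5 = 243 health states and the SAP's coding allows 5^5 = 3125. Under the SAP's coding the index runs from 1 (11111) to 1 - 1.573 = -0.573 (55555), and the misery score from 5 to 25.

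**Matching by text.** Unable (self-care, usual activities), extreme pain and extremely anxious correspond to SAP level 5. Moderate pain and moderately anxious correspond to level 3. The three *some problems* answers and *confined to bed* have no counterpart.

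**Every middle box ticked**, pain and anxiety coded 3:
- *some* = 2: 1 - (0.096 + 0.089 + 0.068 + 0.098 + 0.123) = 0.526
- *some* = 3: 1 - (0.122 + 0.107 + 0.101 + 0.098 + 0.123) = 0.449
- *some* = 4: 1 - (0.237 + 0.220 + 0.255 + 0.098 + 0.123) = 0.067

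The same answers thus differ by up to 0.526 - 0.067 = 0.459. Numbering the boxes 1-2-3 instead gives state 22222 and 1 - 0.370 = 0.630.

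**Every worst box ticked:**
- Boxes numbered 1-2-3 (33333): 1 - 0.551 = 0.449. The range is 0.551 of 1.573 (65% lost) and the misery maximum is 15.
- By text, *confined to bed* = 5: -0.573. No range is lost and the misery maximum is 25.
- By text, *confined to bed* = 3: 1 - (0.122 + 0.261 + 0.255 + 0.414 + 0.321) = -0.373. The range is 1.373 of 1.573 (13% lost) and the misery maximum is 3 + 4 × 5 = 23.

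**The case against.** The strongest reply is that the documents show a wrong sample page and do not show wrong data. Protocol 8.2.11 points to a source worksheet and does not cite Appendix G. The SAP says it was written from eCRF version 14.2.2 and the app specifications, neither of which is available here, and it then lists five coded answers. That suggests five-level capture, without proving it. This stands, and it makes the consequences conditional.

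A reader might infer from the 1-2-3 coding that the index loses 65% of its range and that the worst states are scored as moderate. No document proposes that coding, and it conflicts with the SAP's own labels for the worst answer in four of the five dimensions. Coding by label gives a loss of 0 to 13%. The firmer problem is the ambiguity of the unmatched answers.

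A reader might also infer that the quality-of-life objective as a whole cannot be met. It can in part: the 0-100 scale is on the printed form and is analysed in SAP 3.6, and the NPRS, another patient-reported outcome, does not depend on this form.

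The documents state no consequence of the UK wording. It is a reason to choose suitable country versions when the page is replaced.

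What the reply does not remove is the contradiction. All five dimensions consistently show three complete statements in wording that differs from the SAP's labels, so a fault in text extraction does not explain it.

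**Conclusion.** The mismatch is certain on the face of the documents: three levels on the printed form, five in the SAP, and no conversion rule. Its effect on the data is unknown. If the printed form was used, the index, dimension summaries and misery score cannot be derived as planned. The size then depends on an assumed coding: 0.067 to 0.526 for a respondent ticking every middle box with moderate pain and anxiety coded 3, and 0.449 down to -0.573 for the worst state. If a five-level worksheet was used throughout, only the appendix is wrong.

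This should be fixed, but it does not threaten the main results. It touches one of six secondary endpoints, summarised descriptively in a registry that tests no formal hypotheses.

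**What to change.** Replace Appendix G with the five-level questionnaire in versions suited to the United States and Canada. Before analysis, confirm from the worksheet template and the eCRF which version was used, and record the answer in the SAP.

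Only if three-level forms turn out to have been used:
- flag the version by subject and visit;
- apply the SAP 4.1 table to five-level forms alone;
- summarise three-level forms separately with a prespecified three-level value set, which neither document now contains;
- calculate change from baseline only where both forms are of the same version.

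**Cost.** The appendix change is a protocol amendment and needs the approvals in Protocol 12.7. Checking the template and eCRF is a small task. If three-level forms are found, the check extends to as many as 200 subjects × 3 time points = 600 worksheets, and some subjects may leave the pooled index summary.

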### **Self-Care**

I have no problems with self-care

I have some problems washing or dressing myself

I am unable to wash or dress myself

### **Usual Activities (e.g. work, study, housework, family or leisure activities)**

I have no problems with performing my usual activities

I have some problems with performing my usual activities

I am unable to perform my usual activities

### **Pain/Discomfort**

I have no pain or discomfort

I have moderate pain or discomfort

I have extreme pain or discomfort

### **Anxiety/Depression**

[figure not shown]
I am not anxious or depressed

I am moderately anxious or depressed

I am extremely anxious or depressed

Best  
imaginable  
health state

100

To help people say how good or bad a health state is, we have drawn a scale (rather like a thermometer) on which the best state you can imagine is marked 100 and the worst state you can imagine is marked 0.

We would like you to indicate on this scale how good or bad your own health is today, in your opinion. Please do this by drawing a line from the box below to whichever point on the scale indicates how good or bad your health state is today.

Your own  
health state  
today

Worst  
imaginable  
health state

## 13.8 Appendix H: Adverse Event Form

# Varithena® Venous Leg Ulcer Registry Adverse Event Reporting Form V01

Please complete the following information:

## Section 1. Patient Demographics

Age: _____ years	Gender:  Male  Female	Ethnic Origin:
Height: _____ cm	Weight: _____ kg	 Caucasian  Hispanic/Latin American  Black/African American  Western Asian  East/Southeast Asian  Other or unknown

## Section 2. Varithena Administration

Treatment: \_\_\_\_\_ mL      Batch Number: \_\_\_\_\_  
Date: \_\_\_\_/\_\_\_\_/\_\_\_\_      Expiry Date: \_\_\_\_\_

### Section 3. Adverse Events

**Continued on a separate sheet?**

Event No.	Adverse Event Term	Dates of Onset & Resolution (dd/mmm/yyyy)		Outcome of Event 	Causal Relationship 
1		Onset	/ /		
		Resolution	/ /		
2		Onset	/ /		
		Resolution	/ /		
3		Onset	/ /		
		Resolution	/ /		
4		Onset	/ /		
		Resolution	/ /		
5		Onset	/ /		
		Resolution	/ /		

(1) Outcome of Event (enter one code per event): 1 = Fatal 2 = Not Resolved 3 = Resolved 4 = Resolved with Sequelae 5 = Resolving  
(2) Causal Relationship to Varithena (enter one code): 0 = "Not related (no reasonable possibility)" 1 = "Related (reasonable possibility)"

**Section 4. Any relevant medical history/concurrent conditions and clinical progression of the adverse event including labs, diagnostics, etc.?**  Y  N *(If yes, specify below)*

**Please email the completed form to BTG Vigilance within 48hrs of awareness to**

# Varithena® Venous Leg Ulcer Registry

## Adverse Event Reporting Form V01

### Section 5. Concomitant medications

Only include drugs given within the 30 days prior to AE onset excluding treatment for AE

Drug Name	Brand	Indication for use	Total Daily Dose Prior to this AE (include units)	Freq.	Route of admin.	Date of First Administration of Drug AND Date of Last Administration of Drug Prior to this SAE (dd/mmm/yyyy)	
						First	/ /
						Last	/ /
						First	/ /
						Last	/ /
						First	/ /
						Last	/ /
						First	/ /
						Last	/ /
						First	/ /
						Last	/ /

### Section 6. Reporter information

HCP Name: \_\_\_\_\_

Position: \_\_\_\_\_

Hospital Name: \_\_\_\_\_

Address: \_\_\_\_\_

\_\_\_\_\_

State: \_\_\_\_\_

Contact details: \_\_\_\_\_

### Form(s) completed by:

Print Name: _____	Signature: _____	Date of Completion: / /
-------------------	------------------	-------------------------

Please email the completed form to BTG Vigilance within 48hrs of awareness to

[[contact]](mailto:[contact])

1.1 Study design

This 12 month, multicenter, open-label registry is designed to collect treatment and outcome data related to patients treated with Varithena® for great saphenous vein (GSV) system and/or anterior accessory saphenous vein (AASV) incompetence resulting in venous leg ulcer (VLU). Patients are treated per Investigator's standard of care (SoC) and in accordance with the full prescribing information (FPI) and instructions for use (IFU). For patients with healed ulcers during the 12 month follow-up period, VLU recurrence information is collected. Wound recurrence is defined as the reopening of a wound that was previously closed; all references throughout protocol to wound recurrence refers to wounds that are at the same location.

Note: In cases of cluster wounds, Investigator collects data for a single, primary wound. If more than one wound meets eligibility criteria, Investigator determines which wound to evaluate as the primary/target wound. All endpoint measurements are collected for the primary wound.

For each patient, participation in the registry lasts approximately 12 months. Patients are seen at the investigational site for initial treatment, about one week after treatment for initial follow-up visit (and retreatment if necessary), 12 weeks (± 1 wk) and 12 months (± 1 wk) after initial treatment. Between follow-up visits, and until wound closure, patients are asked to collect weekly photographs of the wound via the subject data capture tool (sDCT) during dressing changes at the wound care center (WCC).

Additionally, follow-up phone calls are placed at 3 months (± 1 wk) post-closure and 6 months (± 1 week) post-treatment. At that time, patients are asked to take a picture of the wound area and complete the numeric pain rating scale (NPRS) using the sDCT.

